Eplerenone is a relatively safe medication, but it can lead to raised serum potassium levels (i.e., hyperkalemia), which can be potentially life-threatening. In a large clinical trial of patients with CHF, the incidence of serious hyperkalemia, defined as a serum potassium concentration ≥ 6 mEq/L, was 5.5% in the eplerenone group and 3.9% in the placebo group. Patients with a lower creatinine clearance at baseline had a higher incidence of serious hyperkalemia.[37]

Eplerenone comes in two doses, 25 mg and 50 mg. The standard dose for treatment of hypertension is 50 mg daily. For patients with an inadequate blood pressure response to 50 mg, the dosage is increased to 50 mg twice daily. For treatment of CHF, patients are started on 25 mg, and escalated to 50 mg within four weeks. Dose adjustment in CHF patients takes place based on serum potassium levels as follows: < 5.0 mEq/L – Increase to 50 mg once daily; 5.0 – 5.4 mEq/L – Maintain dose; 5.5 – 5.9 mEq/L – Decrease to 25 mg every other day; ≥ 6.0 mEq/L – Withhold and restart at 25 mg every other day when potassium levels fall to < 5.5 mEq/L.[38]

The other notable side effects with aldosterone-receptor antagonist medications are related to cross-reactivity with sex hormone receptors. Eplerenone has a much lower incidence of anti-sex hormone effects than spironolactone. With eplerenone, sex hormone-related events, such as breast enlargement in men, breast pain, or menstrual abnormalities, have been reported in up to 2.5% of patients, although some studies reported no such events.[39-41]

Because of the elevations in serum potassium concentrations and consequent increased risk for hyperkalemia with eplerenone, use of this drug is contraindicated in patients at increased risk for hyperkalemia, including those with a serum potassium concentration > 5.5 mEq/L, type 2 diabetes and microalbuminuria, a serum creatinine concentration > 2 mg/dL in men and > 1.8 mg/dL in women, or a creatinine clearance < 50 mL/min, and during concomitant administration of potassium supplements, potassium-sparing diuretics, and/or potent CYP3A4 inhibitors.[38] It is recommended to check serum potassium and creatinine before initiating eplerenone therapy, followed by serum potassium within the first week and at one month after the start of treatment.[38]

Part II

Experimental Protocol:

Study Design

[figure not shown]
- Prospective, consecutive, non-randomized, non-blinded, non-comparative interventional pilot study

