Both male and female participants of any race will be enrolled.

Inclusion Criteria:

1. Age 18 or over
2. Ability to give written informed consent
3. Presence of sub-retinal fluid under the fovea as seen on OCT
4. Diagnosis of Acute or Chronic CSCR:
 - a. Acute CSCR: First presentation to eye clinic with visual symptoms, including decreased vision or visual distortion, and the characteristic appearance of CSCR on examination, fluorescein angiography, and OCT.
 - b. Chronic CSCR: Previous diagnosis of CSCR, persistent subretinal fluid on OCT \geq 3 months after initial presentation to the eye clinic, and <50%

reduction in fluid thickness on OCT after 3 months. *Patients who have had previous treatment for CSCR may be included.*

Exclusion Criteria:

1. Age less than 18
2. Persons with impaired decision-making ability.
3. Women who are known to be pregnant or are actively trying to conceive.
4. Additional eye disease affecting the macula or posterior retina.
5. At screening, serum potassium concentration ≥ 5.0 mEq/L, a serum creatinine concentration >2 mg/dL in men and >1.8 mg/dL in women, or a creatinine clearance <50 mL/min, and during concomitant administration of potassium supplements, potassium-sparing diuretics, and/or potent CYP3A4 inhibitors (amifostine, cyclosporine, fluconazole, itraconazole, ketoconazole, mifepristone, posaconazole, potassium salts, Rituximab, tacrolimus, voriconazole, nefazodone, troleandomycin, clarithromycin, ritonavir, or nelfinavir).
6. Patients with type 2 diabetes will be screened for microalbuminuria with a urinalysis. If microalbuminuria is present, these patients will be excluded.

Data Elements

The data elements to be collected from each participant include age, gender, visual acuity, intraocular pressure, lens status, and retinal examination findings, color fundus photographs, fluorescein angiography images, and OCT images.

Primary Outcome

Presence or absence of subretinal fluid and/or intraretinal fluid on OCT after 4 weeks of treatment with 50 mg of eplerenone.

Secondary (Exploratory) Outcomes

- Change in central macular circle thickness on OCT, automatically calculated with OCT software after 1, 2, and 4 weeks of treatment
- Change in thickness of subretinal fluid under the fovea on OCT, manually calculated after 1, 2, and 4 weeks of treatment
- Change in thickness of choroid under the fovea on enhanced-depth imaging OCT, manually calculated, after 1, 2, and 4 weeks of treatment

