 The maximum number of participants over the entire study is expected to be 20.
3. Will participants receive any payment or other compensation for participation?
 No. There are no costs to subjects participating in this research study and he or she will not be billed for the visit. Eplerenone will be provided by the New England Eye Center.
4. Will participants be studied outside NEEC premises?
 No.

5. Will the facilities of the Clinical Research Center be used?
No.
6. Will drugs be used?
Yes. Eplerenone 50mg, an oral medication FDA-approved for use in systemic hypertension and congestive heart failure, will be used off-label for treatment of all patients in this study. Patients will be provided the medication by the investigational team. Funding is being provided by the Research Fund of the Ophthalmology Department at Tufts Medical Center.
7. Will radiation or radioactive materials be employed?
No.
8. Will special diets be used?
No.
9. Will participants experience physical pain or stress?
While some patients experience distorted vision as a result of CSCR, no additional physical distress to patients is expected as a result of this study.
10. Will a questionnaire be used?
No.
11. Are personal interviews involved?
No.
12. Will participants experience psychological stress?
No.
13. Does this study involve planned deception of participants?
No.
14. Can information acquired through this investigation adversely affect a participant's relationships with other individuals?
No.
15. Please explain how subjects' anonymity will be protected, and/or confidentiality of data will be preserved.
The data obtained from the study will be retained by [name] and will be stored at NEEC for a minimum of 8 years per institutional policy. Members of the research study team including the principle and co-investigators will analyze the data. If results of this study are reported in medical journals or at meetings, subjects will not be identified by name, by

recognizable photograph, or by any other means. The subjects' medical records will be maintained according to the NEEC requirements.

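### The protocol does not say who reads the OCT scans or that readers are masked to visit, which leaves the primary fluid call and two manual thickness outcomes open to expectation bias

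*Combined protocol and SAP*

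**What the plan says.** Part II, Study Design, describes the trial as a "Prospective, consecutive, non-randomized, non-blinded, non-comparative interventional pilot study". The Primary Outcome is "Presence or absence of subretinal fluid and/or intraretinal fluid on OCT after 4 weeks of treatment with 50 mg of eplerenone", and Statistical Analysis reports it as a proportion with a 95% confidence interval.

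Under Secondary (Exploratory) Outcomes, two OCT entries are hand measurements: "Change in thickness of subretinal fluid under the fovea on OCT, manually calculated after 1, 2, and 4 weeks of treatment" and "Change in thickness of choroid under the fovea on enhanced-depth imaging OCT, manually calculated, after 1, 2, and 4 weeks of treatment". A third is produced by the device: "Change in central macular circle thickness on OCT, automatically calculated with OCT software after 1, 2, and 4 weeks of treatment". Best-corrected acuity and angiographic leakage are also listed.

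On who handles the data:
- The Data Safety and Monitoring Plan makes the principal investigator and co-investigators responsible for collecting the data and gives only the investigators access to the code key.
- Part III, item 15, adds: "Members of the research study team including the principle and co-investigators will analyze the data". It assigns one numeric code per patient, in chronological order, and keeps all data within the institution.

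Study Visits, item 4, specifies the OCT device and the scan patterns. No section names the person who reads the scans, masks that person to visit, provides a second grader, or defines what counts as absence of fluid.

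**The concern.** Whether a thin residual layer of fluid is present, and where a hand-placed caliper goes, are judgements. A reader who knows that a scan is from week 4 of a treatment expected to work may tend to call an equivocal eye dry. The expectation is on record: Part I hypothesises that fluid will resolve, and the precision table is built on response rates of 70% to 90%.

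The open-label design does not make this unavoidable. It means that patients and clinicians know the treatment; it does not require the scan reader to know the visit. Because there is no concurrent arm, a lenient week-4 call has nothing to cancel against. Statistical Analysis says the results may be used to design later, more rigorous trials, so an inflated proportion could carry forward into their assumptions.

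The protocol takes more care elsewhere. Acuity, a secondary endpoint, gets a standardised protocol and certified examiners (Study Visits, item 3), and Part IV, section B, asks staff not to introduce bias when asking about adverse events. The primary outcome has no equivalent safeguard.

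**Working it through.** **Which outcomes depend on a human reading**
- Fluid present or absent at week 4 (primary): a reading of the scan, with no reader or masking stated.
- Subretinal fluid thickness and choroidal thickness: manual, with no reader or masking stated.
- Central macular circle thickness: calculated by software, so less exposed.
- Acuity: certified examiners, masking not stated. Angiographic leakage: an image reading, masking not stated.

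**Does the existing code mask the visit?** No. It identifies the patient and is one code for all of that patient's visits. It protects confidentiality and does nothing to hide whether a scan is from baseline or week 4.

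**The plan's own precision figures.** Sample Size and Precision Calculations uses exact intervals: lower limit = Beta quantile(0.025; x, n − x + 1), upper limit = Beta quantile(0.975; x + 1, n − x). With n = 10 and x = 7 this gives 0.348 to 0.933, width 0.586, as printed. All six rows of the table reproduce. Nothing here disputes those figures.

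**Effect of one changed call.** The planned enrolment is 20, so one call moves the proportion by 1/20 = 5 percentage points. Around the 70% used in the precision calculation:

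| Eyes called dry | Proportion | Exact 95% CI |
|---|---|---|
| 13/20 | 65% | 40.8% to 84.6% |
| 14/20 | 70% | 45.7% to 88.1% |
| 15/20 | 75% | 50.9% to 91.3% |

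**Effect of a systematic lean.** Assume that a share f of eyes with residual fluid is called dry and that no dry eye is called wet. The expected observed proportion is then p + f(1 − p). The documents give no value for f; the range is an assumption.

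| True p | f = 5% | f = 10% | f = 20% |
|---|---|---|---|
| 0.20 | 0.24 | 0.28 | 0.36 |
| 0.70 | 0.715 | 0.73 | 0.76 |

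For example, 0.20 + 0.10 × 0.80 = 0.28. The inflation is f(1 − p), so it is largest when few eyes have truly resolved.

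**Size of the regrading task.** 20 patients × 4 visits = 80 study-eye visits.

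**The case against.** The best defence is that this is a small descriptive pilot, openly declared non-blinded and non-comparative, and that the larger threat is spontaneous resolution without a control, which masked reading cannot touch. Masking to visit is also imperfect here. Every eye has subfoveal fluid at entry (Inclusion Criteria, item 3), so a dry or nearly dry scan is recognisably post-baseline whatever label is stripped. Patients come from the investigators' own practices (Part III, item 1), so with 20 of them a grader may recognise a scan, and the documents do not establish that an uninvolved qualified grader is available. All of this stands. It limits what masking can achieve, but it does not explain leaving the primary reading without any safeguard when a partial one is cheap.

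A reader might infer three stronger points that the documents do not support:
- *That investigators aware of the visit do read the scans.* The protocol is silent. The statement that team members analyse the data sits in an answer about confidentiality and does not assign image grading.
- *That these readings are the only efficacy evidence.* Software-calculated thickness, acuity and angiography are also listed, and the software measure gives a partial cross-check from the same eyes and visits.
- *That a couple of misreads would turn the result positive.* Going from 7/20 (exact 95% CI 15.4% to 59.2%) to 9/20 (23.1% to 68.5%) lifts the lower limit past the roughly 20% untreated one-month rate in Part I, Prognosis of CSCR, but that pair is hand-picked. At 8/20 the lower limit is 19.1%; two misreads from 4/20 give 6/20, with a lower limit of 11.9%; and 14/20 is already far above 20%. The plan sets no threshold and no test, the 20% applies to acute disease only while the cohort is mixed, and the same section gives 10% or less at the site, which 7/20 already exceeds.

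**Conclusion.** The gap is real and worth closing. No reader is named and no masking to visit is planned, so the primary fluid call and the two manual thickness changes are open to expectation bias in a study with no control arm. The arithmetic supports only this much: 5 percentage points per changed call at 20 patients, and an upward shift of f(1 − p) if a share f of wet eyes is called dry. The value of f is unknown, so the size of the bias cannot be stated, and the documents do not show that any bias would occur. The precision figures are correct and the software-calculated thickness is less exposed. Masked reading would reduce reader bias; it would not remove it, nor help separate drug effect from spontaneous resolution.

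**What to change.** Add a short paragraph to the OCT item under Study Visits that says who reads the scans and how:
- After the last patient's last visit, an existing coordinator exports all study-eye scans under new random scan-level codes, with patient code and visit date removed. The per-patient codes should not be reused, because they keep each eye's series together.
- An existing co-investigator, preferably one who did not treat that patient, grades fluid presence and measures subretinal fluid and choroidal thickness in random order.
- These readings are the ones used for the primary and the manual secondary outcomes. Reading at visits for clinical care continues unchanged.

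This stays in-house, as Part III, item 15, requires, and needs no new staff, scans or patients. The cost is a short batch regrading of about 80 study-eye visits and a delay in the efficacy readings until the scans are batched. The report should say that masking was partial, because a dry scan cannot be a baseline scan, and should show the software-calculated thickness alongside the manual measures.

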Of note, even after fluid resorption, visual changes may still be reported by patients for several months after the initial episode.[15] The definition of chronic CSCR has not been agreed upon, but most of the literature defines it as sub-retinal fluid lasting more than 3 months, or recurrence of the disease within 1 year.[8-12] Chronic CSCR is also more likely to be bilateral, while acute CSCR more typically affects one eye at a time. Approximately 30-50% of all CSCR patients have recurrences of the disease, either in the same eye, opposite eye, or both eyes.[8,12] Patients with chronic CSCR can also develop intra-retinal fluid in addition to sub-retinal fluid.

Pathophysiology of CSCR

The pathophysiology of CSCR remains unclear, but recent studies using specialized imaging techniques have been helpful. CSCR is thought to be caused by an underlying abnormality in vascular permeability in the choroidal vessels, leading to elevation of the retinal pigment epithelium (RPE) from Bruch's membrane. The separated RPE may then undergo tiny rips, leading to direct connection between the choroid and the subretinal space. The RPE pump, which usually prevents accumulation of fluid under the retina, then dysfunctions or is overwhelmed, leading to build-up of serous fluid under the retina, the typical and characteristic feature of CSCR.[8,12] The abnormality in choroidal circulation is often bilateral. A familial predisposition is occasionally observed, although no clearly-defined pattern of inheritance has been elucidated.

Imaging in CSCR

Specialized imaging techniques are typically used to diagnose and follow patients with CSCR. Fluorescein angiography (FA) is the gold standard to diagnose the disease. The most characteristic finding is an expanding point of fluorescein leakage under the neurosensory detachment of the macula, seen in approximately 90% of patients.[8] Multiple points of leakage can be seen in some patients, particularly in chronic CSCR.[16] FA can be used to direct focal laser photocoagulation treatment or photodynamic therapy (both discussed below).

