- Eligible patients will be those who present with CSCR, both acute and chronic types
- 20 patients will be enrolled; participation is voluntary and all interested patients must provide written informed consent to take part in the study

- Chronic CSCR will be defined as persistent subretinal fluid on OCT ≥ 3 months after initial presentation to the eye clinic, and $< 50\%$ reduction in fluid thickness on OCT after 3 months.
- Only one eye of a participant will be included in the study, although both eyes will be evaluated. In patients with bilateral CSCR, the worse eye will be the study eye.
- Patients will be evaluated and treated at the New England Eye Center (NEEC)
- All participants will receive a standard ophthalmic examination as well as color fundus photographs, fluorescein angiography, and macular OCT (see below for specific imaging protocol).
- Treatment will be the standard dose of eplerenone, 50 mg pills taken one pill daily over four weeks
- Subjects participation will include 4 visits to the NEEC:
 - o Treatment initiation
 - o 1 week after initiation
 - o 2 weeks after initiation
 - o 4 weeks after initiation
- Prior to initiating treatment, all subjects will have laboratory testing to confirm healthy ranges of the following lab tests will include: serum potassium, creatinine, electrolytes, liver function tests, uric acid, and fasting cholesterol.
- Serum potassium and creatinine levels will be re-tested at the 1 week visit.
- All lab tests will be repeated at the 4 week visit
- Blood pressure will be measured at each visit
- A database of enrolled participants will be maintained on a password protected desktop computer at the New England Eye Center.
- When the study is complete, all data will be de-identified and coded.

Study Assessments/Schematic

Study Protocol

-4 to 5 weeks total
 -20 patients with CSCR (Acute or Chronic)

Initial Diagnosis and Enrollment

1. In order to diagnose CSCR, patients typically undergo a routine ophthalmic examination, fundus photographs, fluorescein angiography, and OCT images. Patients may undergo fundus autofluorescence testing or indocyanine green angiography at the discretion of the physician to confirm the diagnosis of CSCR. These tests are done routinely in the eye clinic and are not included as part of the study protocol.

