- Change in best-corrected visual acuity before and after 4 weeks of treatment
- Change in dye leakage characteristics on fluorescein angiography before and after 4 weeks of treatment
- Change in the same OCT characteristics listed above, in the fellow eye
- Proportion of acute vs. chronic CSCR patients
- Safety and tolerability characteristics in this patient population via clinical laboratory data, blood pressure, and adverse events

Data Safety and Monitoring Plan

See below for details regarding monitoring of adverse events (AEs) and serious adverse events (SAEs). Data will be monitored with the patients' safety in mind. All adverse effects will be recorded by the Principal Investigator and Co-Investigators and will be reported to the IRB at the conclusion of the study. Should an SAE occur, it will be reported immediately to the Tufts MC / TUHS IRB by the Principal Investigator within 24 hours. The Principal Investigator and Co-Investigators will be responsible for collecting the patient data information. The information will then be de-identified and coded. The key to the code will only be accessed by the investigators.

Dose adjustment and/or stopping criteria

Serum potassium criteria

If serum potassium is ≥ 5.0 mEq/L and < 5.5 mEq/L at 1 week after initiation, dosing will be decreased to 25 mg every day and serum potassium will be rechecked at 1 week. If serum potassium is still ≥ 5.0 mEq/L and < 5.5 mEq/L after 1 additional week, dosing will be decreased to 25 mg every other day and serum potassium will be rechecked at 1 week. If serum potassium is still ≥ 5.0 mEq/L and < 5.5 mEq/L after 1 additional week, dosing will be withheld. If serum potassium is ≥ 5.5 mEq/L at 1 week, eplerenone will be withheld.

See below for definition of adverse events and serious adverse events.

Statistical Analysis

The primary outcome will be described by the proportion of patients without subretinal fluid on OCT at the end of the study period (see below for sample size and precision estimates). The 95% confidence interval (CI) for this proportion will also be estimated. Descriptive statistics are considered appropriate for this pilot study since there is currently no standard treatment for CSCR, and the data from this study may be used to design future, rigorous trials of eplerenone.

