Changes in continuous secondary outcome measures will be described using mean, median, min/max, and standard deviations, and categorical secondary outcome measures will be described using frequencies and proportions.

Sample Size and Precision Calculations

The natural history of acute CSCR is to improve on its own. Studies have shown, however, that fluid resolution typically takes at least 6 weeks, and often takes as long as 3 months or longer. In a randomized study by Chan et al examining effects of half-dose photodynamic therapy in patients with acute CSCR, 20% of patients had complete resolution of fluid on OCT after 4 weeks, compared to 80% of patients treated with PDT.[12] Similar rates of complete fluid resolution have been reported after treatment with PDT, as well as in a small sample of patients with chronic CSCR treated with eplerenone.[1, 22-26] Based on these assumptions, a calculation was performed to determine the width of confidence intervals for the proportion of patients successfully

treated with eplerenone. If the treatment is effective for 70% of patients, a sample size of 10 patients will give a 95% confidence interval width of 0.586 that includes a lower bound of 0.348 (see range of widths with sample sizes of 10 and 15 below). The Research Design Center of the Clinical and Translational Sciences Institute at Tufts Medical Center assisted with these calculations.

Numeric Results for Two-Sided Confidence Intervals for One Proportion Confidence Interval Formula: Exact

Confidence Level	Sample Size (N)	Target Width	Actual Width	Proportion (P)	Lower Limit	Upper Limit	Width if P = 0.5
0.950	10		0.586	0.700	0.348	0.933	0.626
0.950	10		0.531	0.800	0.444	0.975	0.626
0.950	10		0.442	0.900	0.555	0.997	0.626
0.950	15		0.487	0.700	0.416	0.903	0.522
0.950	15		0.438	0.800	0.519	0.957	0.522
0.950	15		0.356	0.900	0.637	0.993	0.522

References

Flleiss, J. L., Levin, B., Paik, M.C. 2003. Statistical Methods for Rates and Proportions. Third Edition. John Wiley & Sons. New York.
 Newcombe, R. G. 1998. 'Two-Sided Confidence Intervals for the Single Proportion: Comparison of Seven Methods.' *Statistics in Medicine*, 17, pp. 857-872.

Safety Analysis

Safety data will be presented in tabular format and will be summarized descriptively.

PART III

1. How will participants be recruited?
 Participants will be recruited from the practices of the primary investigator and co-investigators.
2. Number of participants needed?

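### Fellow-eye OCT change is summarised without a split by baseline fluid, so the mean change in fluid thickness depends on how many fellow eyes were dry and can offset response against new fluid

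*Combined protocol and SAP*

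**What the plan says.** The combined protocol and SAP lists, under Secondary (Exploratory) Outcomes, "Change in the same OCT characteristics listed above, in the fellow eye". The measures listed above that line are central macular thickness, thickness of subretinal fluid under the fovea, and subfoveal choroidal thickness, each at 1, 2 and 4 weeks.

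Under Statistical Analysis, "Changes in continuous secondary outcome measures will be described using mean, median, min/max, and standard deviations". No section restricts or splits the fellow eyes by their state at baseline, and none makes new fluid in the fellow eye an outcome. The outcomes list asks for the proportions of acute and chronic patients, but not for the number with fluid in both eyes.

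Other relevant statements:

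- Study Design: "20 patients will be enrolled"; "Only one eye of a participant will be included in the study, although both eyes will be evaluated". When both eyes are affected, the more affected one is taken as the study eye.
- Inclusion criterion 3 requires subfoveal fluid without naming the eye. Since each patient has one study eye, I read it as applying to that eye.
- Prognosis of CSCR, on laterality: "Chronic CSCR is also more likely to be bilateral, while acute CSCR more typically affects one eye at a time". On recurrence, the same section says: "Approximately 30-50% of all CSCR patients have recurrences of the disease, either in the same eye, opposite eye, or both eyes".
- Pathophysiology of CSCR: "The abnormality in choroidal circulation is often bilateral".
- Study Visits, OCT item: both eyes are imaged, and OCT is done at every visit.

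**The concern.** The study-eye measures are carried over to fellow eyes that did not have to meet the same entry condition. Every study eye starts with subfoveal fluid, so its fluid thickness can fall. A fellow eye may start with none. Fluid thickness cannot go below zero, so such an eye can contribute only no change or an increase. In an affected fellow eye, a fall is the response of interest. One mean over both kinds of eye describes neither, and its size depends on the mix of patients who happened to enrol.

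New fluid in a previously dry fellow eye is a different event from response in an affected one. In a mean the two have opposite signs and cancel.

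The Statistical Analysis section says the data may help to design later trials of the drug. A small fellow-eye mean could be carried forward as a weak effect when it reflects only how many fellow eyes were dry.

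**Working it through.** **The plan's own figures.** The document states no figure for the fellow-eye outcome. Its only design calculation is the exact confidence interval table for the primary proportion. All six rows reproduce (for example n = 10, p = 0.70: 0.348 to 0.933, width 0.586), but the table has no bearing on this point.

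**Inputs from the document.** N = 20 patients, hence at most 20 fellow eyes. The numbers of fellow eyes with baseline fluid, of eyes with new fluid, and the sizes of change are not given, so they are assumptions below.

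**Formula.** Let B be the number of fellow eyes with baseline subfoveal fluid, d their mean change, m the number of dry eyes that develop fluid, and e their mean change. All other eyes change by 0.

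Pooled mean = (B × d + m × e) / 20

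With m = 0 this is (B/20) × d, so the retained fraction is the share of fellow eyes with fluid, whatever the value of d.

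**Illustration, d = -100 and e = +100 microns (assumed).** The mean among eyes with baseline fluid is -100 in every row.

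| B | m | Pooled mean | Median | SD | Min / max |
|---|---|---|---|---|---|
| 2 | 0 | -10 | 0 | 30.8 | -100 / 0 |
| 4 | 0 | -20 | 0 | 41.0 | -100 / 0 |
| 8 | 0 | -40 | 0 | 50.3 | -100 / 0 |
| 12 | 0 | -60 | -100 | 50.3 | -100 / 0 |
| 2 | 2 | 0 | 0 | 45.9 | -100 / 100 |
| 4 | 2 | -10 | 0 | 55.3 | -100 / 100 |
| 6 | 2 | -20 | 0 | 61.6 | -100 / 100 |

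For example, B = 4, m = 0: (4 × -100)/20 = -20. For B = 2, m = 2: (2 × -100 + 2 × 100)/20 = 0. The median stays at 0 for every B below 10 in this illustration.

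**What min/max and SD add.** With no new fluid, min/max is the same from B = 2 to B = 12, and the SD is the same at B = 8 and B = 12. With two new-fluid eyes the maximum turns positive, which signals new fluid but does not say in how many eyes.

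**How large could the share with fluid be?** Let n_c be the number of chronic patients, a the share of acute patients with fluid in both eyes, and c the same share in chronic patients. Share = ((20 - n_c) × a + n_c × c)/20. Assumed ranges are a = 5-20% and c = 20-80%.

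- All acute: 5-20%.
- Ten chronic: from (10 × 0.05 + 10 × 0.20)/20 = 12.5% to (10 × 0.20 + 10 × 0.80)/20 = 50%.
- All chronic: 20-80%.

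Under these assumptions dry fellow eyes are the majority in an acute sample, and at least half in an evenly mixed one. They can be a minority in a mainly chronic sample.

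**The case against.** The strongest reply is that little depends on this outcome. It is labelled exploratory, in an uncontrolled pilot that is descriptive by design; it carries no test and does not feed the primary proportion or the sample size. The plan never says that all fellow eyes are pooled; that is the default reading of its silence. It also reports min/max and SD, which would show a fall in some eyes and a rise in others. The all-fellow-eye mean is a legitimate quantity, though a different one from response in affected eyes. All of this stands. It limits the weight of the point but does not remove it, because the planned summaries still cannot say how many fellow eyes responded or developed fluid.

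A reader might also infer more than the documents support:

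- **That most fellow eyes will be dry.** The background supports this for acute disease only. It says chronic disease is more likely to be bilateral, and it gives neither a bilateral rate nor the acute/chronic mix.
- **That all three thickness measures are diluted.** Choroidal thickness has no such floor. The choroidal abnormality is described as often bilateral, and the protocol hypothesises choroidal thinning on a systemic drug, so a fluid-free fellow eye can still be informative.
- **That a real response would look like no effect.** With no new fluid the mean is reduced but not zero, and the minimum would show falls. A zero mean needs offsetting new fluid.
- **That 30-50% of fellow eyes might develop fluid during the study.** That figure has no time frame and combines recurrence in the same eye, the opposite eye and both. It shows that opposite-eye disease occurs, not how often in four weeks.
- **That 100 microns is a plausible fall.** The worse eye is the study eye, so affected fellow eyes are the milder ones. The figure only sets a scale.

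**Conclusion.** The point holds for subfoveal fluid thickness, and for central macular thickness so far as it reflects fluid. Taken as written, the plan gives a fellow-eye mean change equal to the mean change in affected eyes multiplied by their share, plus any contribution from new fluid. The direction follows from the floor at zero and needs no outside figure.

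The size is not known. With 4 or 8 of 20 fellow eyes affected and no new fluid, the pooled mean is 20% or 40% of the mean change in affected eyes; those counts are assumptions. The result also assumes that dry eyes otherwise stay unchanged.

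This is a minor improvement to an exploratory summary. It is no flaw in the design and does not affect the primary outcome.

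**What to change.** Add a few lines to Statistical Analysis, using the OCT from the Treatment Initiation Visit as the baseline:

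1. Report change in subfoveal fluid thickness and central macular thickness separately for fellow eyes with and without subfoveal fluid at baseline, with the number of eyes in each group. List individual values where numbers are small. Defining the split by subfoveal fluid matches the measure: an eye with only extrafoveal or intraretinal fluid has a subfoveal fluid thickness of zero and would bring the floor back into the affected group.
2. Among fellow eyes with no subretinal or intraretinal fluid at baseline, report the number and proportion with new fluid by week 4.
3. Keep choroidal thickness change for all fellow eyes.

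No new data are needed, because both eyes are already scanned at each visit. The cost is small subgroups: if 4 of 20 fellow eyes have baseline fluid, the first group is four eyes and should be shown as individual values. The primary outcome and the sample size do not change.
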